5 INVESTIGATIONAL PLAN

5.1 Overall design

This is a multicenter, Phase II study evaluating the efficacy and safety of the combination of lenalidomide and eltrombopag in low risk MDS. This study will include patients with low risk MDS (IPSS low and Int-1) with symptomatic anemia or transfusion dependence. Patients will be treated in 2 separate arms based on their baseline platelet counts:

Arm A : Patients with platelet counts $\geq 50k$ at baseline:

These patients will start Len at 10mg/d for 3 weeks/month, and will not start Eltrombopag until the platelet counts drop below 50,000. If platelets drop less than 50,000, Len will be stopped and Eltrombopag will be started at a dose of 100mg initially and titrated up (similar schema to 509 study) to achieve a platelet count above 50,000. Once the platelet count above 50,000 is achieved, the same dose of Eltrombopag will be continued for an additional two weeks. Once a platelet count $> 50,000$ is maintained for two weeks, Eltrombopag will be discontinued and Len will be started as a single agent. If the plts again fall below 50k then Len will be stopped and Eltrombopag will be re-initiated at the dose that was last given to the patient. Once the platelets are increased to above 50,000 and maintained at this level for 2 weeks, Len will be started again and this time will be given concurrently with Eltrombopag. These agents will now be used concurrently for all subsequent cycles.

Arm B: Patients with Plts $< 50k$ at baseline

These patients will not receive Len initially. Eltrombopag will be started alone at a dose of 100mg initially and titrated up (similar schema to 509 study) to achieve a

platelet count above 50,000. Once the platelet count above 50,000 is achieved, the same dose of eltrombopag will be continued to additional two weeks. Once the plt count > 50,000 is maintained for two weeks, the patients will discontinue eltrombopag and follow the treatment algorithm described for patients in arm A. Patients that never drop their platelet counts below 50,000 will not receive any additional eltrombopag. (Figure 1)

Treatment with myeloid growth factors is permitted for the management of neutropenia at the discretion of the treating investigator.

Study drugs will be continued until disease progression or unacceptable toxicities.

Bone marrow examinations will be performed at baseline, at every 4 months and at study discontinuation.

52 evaluable adult subjects with MDS will be evaluated.

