8.1.2 Dose Modifications

Dose Reductions for lenalidomide

Table 1 gives the dose levels for the dose reduction steps for adverse events.

Table 1: Dose Reduction Steps for lenalidomide

Starting dose 10 mg/day on days 1-21, followed by 7 days of no therapy

Dose level -1 5 mg daily

Dose level -2 5 mg every other day (qod)

Patients who experience limiting neutropenia after prolonged treatment with 5 mg every other day may resume treatment at the same dose upon hematologic recovery.

Dose Modifications for Neutropenia

Hold lenalidomide for a decline in neutrophil count to $< 500/\mu\text{L}$ that does not respond to myeloid growth factor administration. Lenalidomide should be resumed at the next dose

reduction step when neutrophil count is $> 500/\mu\text{L}$. **Dose Modifications for Thrombocytopenia**

For patients with a baseline platelet count $< 50,000/\mu\text{L}$;

Start eltrombopag when the platelet count is $< 50,000/\mu\text{L}$. Start Lenalidomide (AND STOP eltrombopag) only after platelet count $> 50,000$ (non transfused) for at least 2 weeks. If platelet fall $< 50,000/\mu\text{L}$ after resuming lenalidomide again then again hold dose and start Eltrombopag again. Once plt count $> 50,000$ for two weeks, then start lenalidomide and give eltrombopag concomitantly.

For patients with a baseline platelet count $\geq 50,000/\mu\text{L}$;

Start Lenalidomide alone. If plt count falls below $50,000/\text{L}$ then follow algorithm as above.

Patients who do not experience platelet recovery within 8 weeks of starting Eltrombopag should be removed from study and complete all off study evaluations.

Dose modifications for hemoglobin levels:

For those patients experiencing a rise in hemoglobin $> 14 \text{ g/dL}$, Lenalidomide should be withheld until the hemoglobin is $< 12 \text{ g/dL}$, at which time treatment can be resumed according to the dose adjustment recommendations in Table 1. For those patients previously adjusted to the lowest CC-5013 (lenalidomide) dose, the CC-5013 (lenalidomide) schedule should be changed to a 2 week treatment schedule every 4 weeks.

Dose Modifications for Other Adverse Events

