11 RESPONSE CRITERIA

MDS Response Criteria: Modified International MDS Working Group (IWG) Criteria for Measurement of Response/Treatment Effect in MDS (20) will be used to assess response.

Complete Remission (CR)

Bone marrow evaluation (>4 weeks): Bone marrow showing \leq 5% myeloblasts with normal maturation of all cell lines. When erythroid precursors constitute < 50% of bone marrow nucleated cells, the percent of blasts is based on all nucleated cells; when there are > 50% erythroid cells, the percent blasts should be based on the non-erythroid cells. This response should last for at least 4 weeks. Dysplasia if present will be noted.

Peripheral Blood Counts (Absolute values must last >4 weeks)

- o Hemoglobin greater than 11 g/dL (untransfused, patient not on erythropoietin).
- o Neutrophils 1000/mm³ or more (not on a myeloid growth factor)
- o Platelets 100 000/mm³ or more (not on a thrombopoietic agent)
- o Blasts – 0%
- o Hematologic improvement should be obtained.

Marrow CR: Bone marrow: < 5% myeloblasts and decrease by > 50% over pretreatment marrow. Peripheral blood: if hematologic improvement occurs, it will be noted in addition to marrow CR

Partial Remission (PR)

All of the CR criteria (if abnormal prior to treatment), except

- o Bone marrow evaluation: Blasts decreased by 50% over pretreatment, b

Stable Disease

Failure to achieve at least a PR, but with no evidence of progression for >8 weeks.

Failure

Death during treatment or disease progression characterized by worsening of cytopenias, increase in the percent of bone marrow blasts, or progression to an MDS FAB subtype more advanced than pretreatment.

Relapse (following a CR or PR)

One or more of the following:

- o Return to pretreatment bone marrow blast percentage.
- o Decrement of > 50% from maximum remission response levels in neutrophils or platelets.
- o RBC transfusion dependence (> 2 units RBC transfusions over an 8 week period) or a reduction in hemoglobin concentration by >1.5 g/dL in the absence of acute infection, gastrointestinal bleeding, hemolysis, treatment hiatus etc.

6. Disease Progression

A 50 % increase in blasts, depending on baseline blastpercent, if confirmed by subsequent BM examination (Fig 5).

- o For patients with < 5% blasts: increase to > 10% blasts
- o For patients with 5% to 10% blasts: > 50% increase to > 10% blasts
- o For patients with 10% to 20% blasts: > 50% increase to 20% blasts

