- o For patients with 20% to 30% blasts: > 50% increase to 30% blasts

Any of the following:

At least 50% decrement from maximum remission/response in granulocytes or platelets

Reduction in Hgb by 2 g/dL

Transfusion dependence

7. Disease Transformation

Transformation to AML (> 30% blasts).

Cytogenetic Response

Requires 20 analyzable metaphases when using conventional techniques. Analysis of data will require 20 metaphases before and after treatment. Fluorescent *in situ* hybridization (FISH) may be used as a supplement to follow a specifically defined cytogenetic abnormality, but it is not a substitute for conventional cytogenetic studies.

Cytogenetic response is defined as follows:

Complete response: Restoration of a normal karyotype in patients with a documented pre-existing clonal (>2 metaphases abnormal) chromosome abnormalities.

Partial response: > 50% reduction in the percentage of bone marrow metaphases with only clonal abnormality.

Hematologic Improvement

Improvements must last >8 consecutive weeks.

1. Erythroid Response

Hgb increase by 1.5 g/dL if not transfusion dependent Relevant reduction of units of RBC transfusions by an absolute number of at least 4 RBC transfusions/8 wk compared with the pretreatment transfusion number in the previous 8 wk. Only RBC transfusions given for a Hgb of 9.0 g/dL pretreatment will count in the RBC transfusion response evaluation

2. Platelet Response

For patients with a pretreatment count < 100,000/mm³, an absolute increase of > 30,000/mm³ (for patients with pretreatment counts >20,000).

For patients with pretreatment counts < 20,000, an increase to absolute count above 20,000 by at least 100% increase will be considered as response.

†;for platelet transfusion-dependent patients, stabilization of platelet counts and platelet transfusion independence.

3. Neutrophil Response

At least 100% increase and an absolute increase $> 0.5 \times 10^9/L$

4. Progression/Relapse Following Erythroid Hematologic Improvement

At least 1 of the following:

At least 50% decrement from maximum response levels in granulocytes or platelets

Reduction in Hgb by 1.5 g/dL

Transfusion dependence

Duration of Response

Time to disease progression (as per Bone Marrow Responses above) or progression/relapse following hematologic improvement (as per Hematologic Improvement above).

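### The relapse rule after erythroid improvement has no exemption for the protocol's own hemoglobin hold, so on the natural reading a responder who completes that hold is recorded as relapsed (minor; secondary endpoint only)

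*Combined protocol and SAP*

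**What the plan says.** Section 11, under Progression/Relapse Following Erythroid Hematologic Improvement, needs only one of three events. They are a count fall ("At least 50% decrement from maximum response levels in granulocytes or platelets"), a hemoglobin fall ("Reduction in Hgb by 1.5 g/dL") and transfusion dependence. The count item names its reference level and the hemoglobin item names none. No item is qualified for time off drug. Duration of Response then runs to disease progression or to "progression/relapse following hematologic improvement (as per Hematologic Improvement above").

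Section 8.1.2, on dose modifications for hemoglobin levels, applies once hemoglobin rises above 14 g/dL: "Lenalidomide should be withheld until the hemoglobin is" below 12 g/dL, after which treatment may resume.

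Two places allow for time off drug. In Section 11, the hemoglobin item for relapse after CR or PR counts a fall only "in the absence of acute infection, gastrointestinal bleeding, hemolysis, treatment hiatus etc". Section 8.1.1 postpones the final response assessment after toxicity delays. Neither changes the erythroid relapse rule.

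Duration of hematologic improvement is a secondary objective (Section 4.1.2).

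**The concern.** One section tells the site to let hemoglobin drift down from above 14 to below 12 g/dL. Another treats a smaller drop as the end of response. A patient managed exactly as instructed could therefore have the duration clock stopped by the dosing rule and not by the disease. Those affected would be the responders with the highest hemoglobin, so the shortening would fall on the best responses. Because the hemoglobin item gives no reference level, sites could also apply it differently, and the durations they report would not be comparable.

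**Working it through.** The plan gives no figure of its own to reproduce here. The check compares thresholds.

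**Inputs**
- Hold starts above 14 g/dL and ends below 12 g/dL (Section 8.1.2).
- Relapse after erythroid improvement: a fall of 1.5 g/dL (Section 11).
- Disease Progression hemoglobin item: a fall of 2 g/dL (Section 11).
- Erythroid response if not transfusion dependent: a rise of 1.5 g/dL (Section 11).
- Entry by the untransfused-anemia route: 10.0 g/dL or below (Section 6.1, item 4).

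**1. Fall brought about by the hold.** Fall = level at start of hold − level at restart, which is more than 14 − 12 = 2.0 g/dL. This exceeds the 1.5 g/dL limit by more than 2.0 − 1.5 = 0.5 g/dL. For a patient held at just above 14, the limit is crossed near 14 − 1.5 = 12.5 g/dL, before the protocol allows lenalidomide to restart.

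**2. Gain still present at restart.** Take a value just below 12. With entry at 10.0, the remaining gain is about 12 − 10.0 = 2 g/dL; with entry at 9 it is about 3, and at 8 about 4. Each exceeds the 1.5 g/dL rise that defines response.

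**3. Dependence on the reference level.** For a patient who entered at 10.0 and is held at just above 14:

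| Fall measured from | Relapse at or below | Just below 12 is relapse? |
|---|---|---|
| Level reached during response | about 14 − 1.5 = 12.5 | Yes |
| Level that first met the response definition (10.0 + 1.5 = 11.5) | 11.5 − 1.5 = 10.0 | No |
| Pretreatment level | 10.0 − 1.5 = 8.5 | No |

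On the last reading, a patient who lost the whole gain would not have relapsed, which cannot be intended. The first reading fits best, because the neighbouring count item is measured from the maximum response level.

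**4. Disease Progression.** A fall of more than 2.0 g/dL also meets the 2 g/dL item in that list. Whether the item can stand without a blast rise is unclear from the layout of the list.

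**5. Frequency.** Section 3.4 reports, for the earlier lenalidomide study, a median sustained hemoglobin of 13.4 g/dL (range 11.5 to 15.8). Sustained values above 14 therefore occur in responders. It does not say how many patients ever rise above 14, which is what triggers the hold.

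**The case against.** The strongest objection is that the hemoglobin item names no reference level, so the conflict is not certain. Measured from the level at which improvement was first established, a fall to just below 12 is not a relapse for a patient who entered at 10.0. That stands, and it is why the conclusion is conditional. It also shows that the rule needs completing.

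A second objection is that the published response criteria on which Section 11 is based may carry a qualifier. That cannot be checked here. Section 11 writes out its own list, and sites will apply what is written.

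A third is that duration is a secondary objective and Section 14 attaches no test, power or decision to it. That is correct and sets the severity.

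Two stronger readings are tempting, and the documents do not support them:

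- **Platelet and neutrophil holds.** A reader might infer the same conflict when platelets drop below 50,000 or neutrophils below 500/µL. There the fall comes first, on lenalidomide, and the hold follows: "If platelets drop less than 50,000, Len will be stopped and Eltrombopag will be started". The neutrophil hold likewise answers a fall "that does not respond to myeloid growth factor administration". These falls trigger the hold; they do not result from it. The count item for relapse after CR or PR has no hiatus exemption either, so there is no precedent in the plan to extend.
- **A number of patients.** A reader might turn the sustained hemoglobin range in Section 3.4 into a count of affected responders. Sustained values do not bound how many patients pass 14 at some time, and that study included 25 mg and 10 mg daily dosing as well as the schedule used here.

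**Conclusion.** The point holds for the hemoglobin hold, as a minor flaw in a secondary endpoint. If the fall is measured from hemoglobin during response, every responder who completes the hold meets the relapse rule by a margin of more than 0.5 g/dL. That includes patients who still have a response-sized gain. The number affected and the effect on median duration cannot be computed from the documents. The primary response rate is unaffected, because the relapse rule applies only after improvement has been established.

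A reader might also infer that the hold makes patients stop study drug (Sections 5.1 and 8.3) and ends their response follow-up (Section 8.4), because the fall also meets the 2 g/dL Disease Progression item. That follows only if the item stands alone, and the text does not settle this.

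**What to change.** Amend the erythroid relapse list in Section 11:

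1. State that the hemoglobin fall is measured from the maximum untransfused hemoglobin during response.
2. Add the treatment-hiatus exemption for hemoglobin falls between the recorded start of a Section 8.1.2 hemoglobin hold and 8 weeks after lenalidomide restarts. Recorded dates, not investigator attribution, should define this window.
3. Still count relapse if the patient becomes transfusion dependent, or if hemoglobin at the end of the window is less than 1.5 g/dL above pretreatment. Date it to the first qualifying fall.
4. Say whether the 2 g/dL Disease Progression item stands alone; if it does, apply the same exemption there.
5. Report duration with and without the exemption.

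The hemoglobin hold has no explicit time limit of its own, so the amendment should also say when the window closes if lenalidomide is never restarted.

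The cost is a short amendment, hold and restart dates on the case report form, and one additional summary. The downside is that true loss of response during a hold may be recognised some weeks late, and reported duration may lengthen slightly. Back-dating limits the first, and the paired report shows the second.

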12 DATA MANAGEMENT

12.1 Analyses and Reporting

Data will be analyzed and reported after 25 patients are enrolled. All subsequent data collected will be analyzed and reported in a follow-up clinical report by the PI.

12.2 Study auditing

12.2.1 Investigator responsibilities

Investigator responsibilities are set out in the ICH guideline for Good Clinical Practice (GCP) and in the US Code of Federal Regulations.

Investigators must enter study data onto CRFs or other data collection system. The Investigator will permit study-related audits by Celgene or its representatives, IRB/EC review, and regulatory inspection(s) (e.g., FDA, EMEA, TPP), providing direct access to the facilities where the study took place, to source documents, to CRFs, and to all other study documents.

13 DATA SAFETY AND MONITORING BOARDS

All trials initiated by Montefiore-Einstein are subject to oversight by the Albert Einstein Cancer Center Data Safety Monitoring Board (DSMB). This board meets once a month with any additional meetings scheduled when needed. The responsibilities are as follows:

- Familiarize themselves with the research protocol (s)
- The DSMB reviews trial performance information such as accrual information.

- Review interim analyses of outcome data and cumulative toxicity data summaries to determine whether the trial should continue as originally designed, should be changed, or should be terminated based on these data.
- The DSMB also determines whether and to whom outcome results should be released prior to the reporting of study results.
- All adverse events are reviewed by the committee, with assurances that these have been in fact sent for review to all pertinent IRBs.
- Review of reports of related studies to determine whether the monitored study needs to be changed or terminated.
- Review major proposed modifications to the study prior to their implementation (e.g., termination, dropping an arm based on toxicity results or other reported trial outcomes, increasing target sample size).
- Following each DSMB meeting, provide the study leadership with written information concerning findings for the trial as a whole related to cumulative toxicities observed and any relevant recommendations related to continuing, changing, or terminating the trial.

The study leadership will provide information on cumulative toxicities and relevant recommendations to the local principal investigators to be shared with their IRB's.

14 BIOSTATISTICAL ANALYSIS

14.1 Safety evaluation

Data from all subjects who receive any protocol therapy will be included in the safety analyses. Subjects who entered the study and did not receive any protocol therapy and had this confirmed, will not be evaluated for safety.

The severity of the toxicities will be graded according to the NCI CTCAE v4.0 whenever possible.

14.2 Sample size and power considerations

The primary outcome is major erythroid response. A maximum of 52 patients will be enrolled into the study. An early stopping rule for lack of efficacy will be implemented as follows based on Simon's optimal two-stage design. After the first 25 patients have been enrolled and evaluated for response, the trial will be terminated early if fewer than 7 patients respond to treatment. If 7 or more responses are observed, the trial will continue until a total of 52 patients have been evaluated. At the end of the trial, the treatment will be considered efficacious and worthy of further study if 17 or more patients respond out of 52 patients.

The target response rate is assumed to be 40%. (Conservative estimate) A response rate less than 25% is considered to be clinically unimportant(21). Under these assumptions, the design specified above has the following operating characteristics. The probability of accepting the treatment for further study if the response rate is unacceptably low

(<25%) is at most 10%. In contrast, there is a 80% probability of accepting the treatment for further study if the response rate is at least 40%. The expected sample size is 32.4 subjects. It is also assumed that 10-20% of patients with plts > 50,000 that receive Len may not need Eltrombopag at all as there plts will not fall below 50,000.

Furthermore, since we will accrue patients with both high and low platelet counts, it is possible that the response rates to Lenalidomide will be different in these groups. These will be analyzed by exploratory studies.

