Appendix 2: ECOG Performance Status Scale

Appendix 3: Cockcroft-Gault estimation of CrCL

Appendix 4: International Prognostic Scoring System (IPSS) for MDS

Appendix 5: NCI CTC Version 4.0

Appendix 6: Correlative Studies

1 PROTOCOL SYNOPSIS

PROTOCOL TITLE:PHASE II STUDY OF LENALIDOMIDE AND ELTROMBOPAG IN PATIENTS WITH SYMPTOMATIC ANEMIA IN LOW OR INTERMEDIATE I MYELODYSPLASTIC SYNDROME (MDS)	
DATE PROTOCOL FINAL:	08 JULY 2011
INDICATION:	MDS
STUDY PHASE:	Phase II

BACKGROUND AND RATIONALE:The rationale for this study is that combined treatment with eltrombopag (PROMACTA) and lenalidomide (REVLIMID) will reduce the incidence of lenalidomide induced thrombocytopenia thus enabling patients to tolerate the required duration of lenalidomide therapy leading to higher rates of response to lenalidomide. A major reason why lenalidomide cannot be used for the treatment of MDS is because of the occurrence of thrombocytopenia. The use of eltrombopag will potentially raise platelet counts in these patients and enable a longer exposure to lenalidomide. Secondly, thrombocytopenia in the first 2 months after lenalidomide therapy predicts the subsequent response to lenalidomide treatment in patients with low risk MDS. Thus raising platelet counts to enable continuation of Lenalidomide therapy is important in these patients. Lastly, an increase in blasts has been a potential concern with the use of thrombopoietin mimetics. Preclinical studies have indicated that eltrombopag is less likely to increase blasts thus making it a possible potential therapeutic candidate in low risk MDS.
	

STUDY OBJECTIVES:
 
Primary Objectives:
 
To evaluate the rate of hematologic improvement of the eltrombopag/lenalidomide combination as defined by the IWG 2006 criteria
 
To evaluate the safety and tolerability of the eltrombopag/lenalidomide combination in patients with low –intermediate risk MDS
 
Secondary Objectives
 
To compare the time to hematologic improvement
 
To evaluate the duration of hematologic improvement
 
To evaluate the effect of combination treatment on platelet counts, platelet transfusions and bleeding events.
 
To evaluate the frequency of bone marrow response (CR+PR) and cytogenetic response.
 
To evaluate the relationship between mutations in bone marrow stem cells and response
 
To evaluate the relationship between various stem and progenitor alterations and response
	

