
STUDY DESIGN:
 
This is a multicenter, phase II study evaluating the efficacy and safety of the combination of lenalidomide and eltrombopag in low risk MDS.
	

Patients will be treated based on their baseline platelet counts:

Arm A: Patients with platelet counts $\geq 50k$ at baseline:

These patients will start Len at 10mg/d for 3 weeks/month, and will not start eltrombopag until the platelet counts drop below 50,000. If platelets drop less than 50,000, Len will be stopped and eltrombopag will be started at a dose of 100mg initially (50 mg for subjects of East Asian heritage) and titrated up to a maximum dose of 300 mg (150 mg for subjects of East Asian heritage) to achieve a platelet count above 50,000/L. Once a platelet count above 50,000 is achieved, the same dose of eltrombopag will be continued for an additional two weeks. Once a platelet count $> 50,000$ is maintained for two weeks, eltrombopag will be discontinued and Len will be started as a single agent. If the platelets again fall below 50,000 then Len will be stopped and eltrombopag will be re-initiated at the dose that was last given to the patient. Once the platelets are increased to above 50,000 and maintained at this level for 2 weeks, Len will be started again and this time will be given concurrently with eltrombopag. These agents will subsequently be used concurrently for all subsequent cycles.

Arm B: Patients with Plts $< 50k$ at baseline

These patients will not receive Len initially. Eltrombopag will be started alone at a dose of 100mg initially and titrated up (Table 4) to achieve a platelet count above 50,000. Once the platelet count above 50,000 is achieved, the same dose of eltrombopag will be continued for an additional two weeks. Once the plt count $> 50,000$ is maintained for two weeks, the patients will discontinue eltrombopag and follow the treatment algorithm described for patients in arm A.

[figure not shown]

Figure 1: Schema of the study (* starting dose of Eltrombopag for Asian subjects is 50mg)

STUDY ENDPOINTS

Primary:

Hematologic improvement

Secondary: Time to attain and duration of hematologic improvement Bone marrow morphologic and cytogenetic response Platelet counts and Bleeding events
	

STUDY DURATION:2 years
	
TOTAL SAMPLE SIZE:52patients

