2 SCHEDULE OF STUDY ASSESSMENTS

	Screening Assessment (30 days prior to initiation)	Weekly	Every 28 days (Day 1 of each cycle)	Week 16 and treatment discontinuation	Follow up ¹¹
Medical History	x				
Prior MDSTreatment	x				
ECOG Performance Status	x	X ⁸	x		
Pregnancy test ¹	x ²		x ³	X	
Serum ferritin level	x			X	
Serum erythropoietin	x				
Thyroid function tests ⁴	x			X	
aaPT/PTT/INR	x				
Serum chemistry ⁵	x	X ⁸	x	X	
Hematology, peripheral blood smear and RBC transfusion history ⁶	x ⁷	x ⁸	x	X	x
Physical examination	x		x	x	x
ECG	x		x ¹²		
Review medication log			x		
Response				x	

assessment ⁹					
Bone marrow aspirate & biopsy ¹⁰	X			X	
Cheek swab and toe nail clipping	X				

1. Women of childbearing potential only. Serum or urine pregnancy testing for β-HCG with a sensitivity of at least 50 mIU/mL. For further requirements for pregnancy testing and birth control, please see Appendix 1.
					

2. Within 7 days prior to the first day of study therapy.
					

3. Every 4 weeks while on study drug.
					

4. TSH (thyroid-stimulating hormone), T3, and T4 levels. Repeat thyroid function tests every three months.
					

5. Includes sodium, potassium, chloride, CO₂, calcium, magnesium, phosphorus, blood urea nitrogen (BUN), creatinine, glucose, albumin, total protein, alkaline phosphatase, total bilirubin, aspartate transaminase (SGOT/AST) or glutamic pyruvic transaminase (SGPT/ALT), lactate dehydrogenase (LDH), and uric acid.
					

6. Red blood cell (RBC) count, reticulocyte count, hemoglobin, hematocrit, white blood cell (WBC) count and differential, absolute neutrophil count (ANC), and platelet count required for protocol therapy must be done < 24 hours prior to the treatment cycle. Pretreatment CBC with differential and LFT's should be done < 1 week before randomization.
					

7. If not obtained within 7 days of the first day of study therapy, repeat the CBC on Day 0 of study treatment prior to start of study therapy.
					

8. Perform weekly for 4 weeks, then every 2 weeks for 5 to 8 weeks and monthly thereafter. Weekly CBC should be done when titrating or starting eltrombopag dosing until a stable platelet count is achieved.
					

9. Hematologic, pathologic, and cytogenetic response will be assessed according to criteria outlined in Section 6.1.2.
					

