Ineffective erythropoiesis remains the hallmark of myelodysplastic syndromes (MDS) for which few treatments offer sustained erythropoietic improvement (13). Lenalidomide (CC-5013; REVLIMID[®]) is an oral 4-amino glutarimide derivative of thalidomide that lacks the neurological toxicities of the parent compound. In a safety and efficacy study (MDS-001) investigating erythroid response to CC-5013 (lenalidomide) monotherapy in 43 patients with MDS, CC-5013 (lenalidomide) yielded a high frequency of major erythroid response (MER) in patients that had either failed prior treatment with erythropoietin or had high endogenous levels and high transfusion burden (14). Patients received treatment with one of three CC-5013 (lenalidomide) dose schedules, 25 or 10 mg daily, or 10 mg/day x 21 days every 4 weeks. Neutropenia (67%) and thrombocytopenia (57%) > grade 3 NCI-CTC version 2.0 were dose limiting, necessitating treatment interruption and dose-reduction in 25 (61%) patients. Other adverse effects were infrequent and of mild to moderate severity including pruritus, fatigue, diarrhea, edema, thyroid dysfunction and joint discomfort. Among the 36 patients completing more than one cycle of treatment, 24 (67%) experienced an erythroid response according to International Working Group (IWG) criteria. MER defined by sustained transfusion-independence (> 8 weeks) or a rise in hemoglobin >2 g/dl was achieved in 21 patients and 3 patients experienced a >50% reduction in red blood cell

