4 STUDY OBJECTIVES AND ENDPOINTS

4.1 Objectives

4.1.1 Primary Objectives

- To evaluate the rate of hematologic improvement of the eltrombopag/lenalidomide combination (as per Modified IWG criteria)
- To evaluate the safety and tolerability of the combination

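### The objectives make hematologic improvement primary, but the only decision rule uses major erythroid response, which is not defined for this trial; the same data could give opposite verdicts

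*Combined protocol and SAP*

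**What the plan says.** All references are to the combined protocol and SAP.

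- **Synopsis, primary objective:** "To evaluate the rate of hematologic improvement of the eltrombopag/lenalidomide combination as defined by the IWG 2006 criteria". HI is also the only item under the primary heading of the synopsis endpoint list. Safety and tolerability is a further primary objective.
- **Section 4.1.1:** "To evaluate the rate of hematologic improvement of the eltrombopag/lenalidomide combination (as per Modified IWG criteria".
- **Section 14.2:** "The primary outcome is major erythroid response". The same paragraph sets a two-stage rule on 25 and then 52 patients. At the first look, "the trial will be terminated early if fewer than 7 patients respond to treatment"; at the end, 17 or more responders count as success. The unacceptable rate is 25% and the target 40%.
- **Section 11:** HI has erythroid, platelet and neutrophil components, each lasting more than 8 consecutive weeks. The erythroid response is not graded, and there is no major category.
- **Section 3.4 (background):** the only description of MER, for an earlier lenalidomide study: "MER defined by sustained transfusion-independence (> 8 weeks) or a rise in hemoglobin >2 g/dl was achieved in 21 patients".

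No section adopts that description for this trial or reconciles the two endpoints. Section 12.1 only schedules a report after 25 patients, and Section 13 describes general DSMB oversight.

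**The concern.** A single-arm phase II trial with a fixed responder count needs one definition of a responder, set before any responses are seen. Here the endpoint in the objectives and the endpoint under the rule have different names and different content. A reader of the synopsis would expect the result on HI; a reader of 14.2 would expect it on MER.

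Two things are at stake. First, the go/no-go decisions at 25 and 52 patients can depend on which section is followed. If the endpoint were settled after responses were known, the stated error rates would no longer apply. Second, the choice affects what the trial measures. The Section 11 platelet response has no requirement that the patient be off thrombopoietic agents, whereas complete remission in the same section does. Eltrombopag is given to raise platelets, and Section 5.1 allows it alongside lenalidomide in all later cycles. Under HI, its direct platelet effect could therefore count as efficacy if it lasted long enough; under MER it could not.

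**Working it through.** **1. Definitions side by side**

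| | MER (Section 3.4, earlier study) | HI (Section 11) |
|---|---|---|
| Hemoglobin | rise above 2 g/dL | rise of 1.5 g/dL if not transfusion dependent |
| Transfusion | independence for more than 8 weeks | at least 4 fewer RBC transfusions per 8 weeks |
| Platelets | not counted | counted |
| Neutrophils | not counted | counted |
| Duration | stated for the transfusion limb; unclear for the hemoglobin limb | more than 8 consecutive weeks |

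**2. Opposite verdicts by direct count**

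- First 25 patients, 5 MER plus 3 platelet-only responders: MER 5 < 7, stop; HI 5 + 3 = 8 ≥ 7, continue.
- All 52 patients, stage 1 passed, 14 MER plus 5 other HI responders: MER 14 < 17, fail; HI 14 + 5 = 19 ≥ 17, succeed.

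**3. The plan's own operating characteristics**

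With X1 the responders among the first 25 and X2 those among the next 27, both binomial with rate p:

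- P(success) = Σ over x1 ≥ 7 of P(X1 = x1) × P(X2 ≥ 17 − x1)
- Expected size = 25 + 27 × P(X1 ≥ 7)

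The printed rule gives 11.8% at p = 25%, 85.6% at p = 40%, and an expected size at 25% of 25 + 27 × (1 − 0.5611) = 36.9. Section 14.2 states at most 10%, 80% and 32.4. Those figures come out (9.92%, 80.03%, 32.38) only if 8 responders are needed to continue. That is a separate matter from the endpoint conflict. Everything below uses the printed boundary of 7.

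**4. Probability that the final verdicts differ**

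If every MER is also an HI, P(differ) = P(success on HI) − P(success on MER). For any other overlap, that difference is the minimum.

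Inputs from Section 3.4, lenalidomide alone:
- without del(5q): MER 27%, major plus minor erythroid response 44%;
- with del(5q): 66% and 75%.

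Major plus minor response stands in for HI. The del(5q) share s is an assumption, since the documents give none. The mixed rates are:
- MER = 27(1 − s) + 66s
- HI proxy = 44(1 − s) + 75s

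| s | MER rate | HI proxy rate | P(success, MER) | P(success, HI proxy) | P(differ) |
|---|---|---|---|---|---|
| 0% | 27.0% | 44.0% | 0.1964 | 0.9438 | 74.7% |
| 10% | 30.9% | 47.1% | 0.4043 | 0.9759 | 57.2% |
| 20% | 34.8% | 50.2% | 0.6313 | 0.9906 | 35.9% |
| 30% | 38.7% | 53.3% | 0.8116 | 0.9966 | 18.5% |

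**5. If MER truly reaches the 40% target**

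Section 3.4 gives three gaps between major and any erythroid response: 3/36 = 8.3 points, 75 − 66 = 9 points, and 44 − 27 = 17 points. Applying them to a MER rate of 40% is an assumption.

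- 48.3%: 0.9833 − 0.8556 = 0.1277 (12.8%)
- 49%: 0.9863 − 0.8556 = 0.1307 (13.1%)
- 57%: 0.9991 − 0.8556 = 0.1435 (14.3% before rounding of the terms)

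**The case against.** The best defence is that 14.2 is clear on its own terms. It opens by naming MER, the rule follows in the same paragraph, and neither the synopsis nor 4.1.1 contains a competing rule. *Respond* there most naturally means MER, and the background says what MER is. This stands in part. A reader might infer that whoever applies the rule has to guess what a responder is, but the text does not support that. What the defence leaves open is that the objectives still say HI, no section gives 14.2 precedence, and the background wording is neither adopted for this trial nor clear about how long a hemoglobin rise must last.

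The probabilities are also open to challenge, and these limits hold:

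- **Population.** The 27% and 44% come from transfusion-dependent patients without del(5q). Sections 6.1 and 6.2 do not exclude del(5q), and untransfused patients can enter. A reader might take 74.7% as this trial's chance of conflicting verdicts; it is only the case with no del(5q) patients.
- **Proxy.** In the first study described in Section 3.4, the responses short of MER were transfusion reductions of more than 50%. Section 11 requires at least 4 fewer transfusions per 8 weeks, restricts which transfusions count, and requires more than 8 weeks. So 44% may overstate or understate erythroid HI. It is tempting to conclude that lenalidomide alone already exceeds the 40% target on HI, but the documents do not show that.
- **Nesting.** HI is broader in most respects, but a brief hemoglobin rise above 2 g/dL might be MER without being HI. The differences in step 4 would then be minimum values.

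**Conclusion.** The plan contradicts itself on its primary efficacy endpoint. HI is primary in the synopsis and 4.1.1. MER is primary in 14.2, where the only stopping and success rule sits, and MER has no operative definition in Section 11. This follows from the text and needs no outside rate.

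The size is illustrative. With the printed boundaries, MER nested in HI and the erythroid proxy, the verdicts differ with probability from 74.7% (no del(5q) patients) down to 18.5% (an assumed 30%), and 12.8% to 14.3% if MER truly reaches 40%. The proxy leaves out platelet and neutrophil responders, who would add to the HI count. The conflict should be settled before the rule is applied at 25 patients.

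**What to change.** Name one primary efficacy endpoint, in identical words, in the synopsis, 4.1.1 and 14.2. Define it in full in Section 11, including its duration requirement. State in 14.2 that *respond* means this endpoint and that the 25% and 40% refer to it. Make the other HI components secondary.

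The choice is the sponsor's:

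- **MER, written out in full:** the 25% and 40% rates and the 52-patient maximum stay as they are.
- **The Section 11 erythroid response, or overall HI:** both rates must be justified again for that endpoint, and the boundaries and possibly the sample size may then change.

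Either erythroid option keeps eltrombopag's direct platelet effect out of the efficacy count.

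The cost is a protocol amendment with the reviews in Section 15.2: both supporting companies, the Einstein IRB and, where scientific quality is significantly affected, the IRB at each center. No new data are needed. An erythroid endpoint may give a lower headline response rate than HI.
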